## **Abstract**

### Introduction

Median sternotomy is currently the main access site for cardiac surgery. Surgical site infection (SSI) of the sternum is a distressing complication in cardiac surgery after median sternotomy. The incidence of postoperative superficial and deep SSI in cardiac surgery varies from 1.3 to 12.8%. Bone wax is a nonabsorbable substance and it is believed that bone wax may cause inflammation and mechanically inhibit osteoblastic activity, which may eventually lead to increased risk of postoperative sternal dehiscence. Sternum Guard™ is a sternal protection device that covers the sternum after median sternotomy, it has specific mechanical protection that prevents lesions on the sternum. Therefore, we would like to evaluate the efficacy of Sternum Guard™ as opposed to Bone wax in post cardiac surgery patients in reducing the surgical site infection, sternal dehiscence and to assess the satisfaction rate of the surgeons.

### Objectives

The aim of the research is to evaluate the efficacy of Sternum Guard™ in post cardiac surgery patient with the application of Sternum Guard™ in comparison with bone wax intraoperatively.

### Method

This study will adopt a single blind, single center, randomized control trial design for 3 months.

### Introduction

#### 1.1 Background

Nowadays, a high volume of cardiac surgery has been performed at National Cardiovascular Centre Harapan Kita, Jakarta, Indonesia. In 2017 there were 1721 cardiac surgery conducted in the adult cardiac surgery division. Of those, 801 were coronary artery bypass graft surgeries, 598 were heart valve repair and replacement surgeries, 93 were vascular surgeries, 116 were congenital cardiac surgeries, 8 surgeries in intracardiac tumour, and 105 other cardiac surgeries.

In cardiac surgeries, the current approach established is through median sternotomy. The sternum consists of a low vascularized tissue and it may be damaged especially when internal thoracic arteries are used for coronary artery bypass grafting. Thus, the postoperative complication related to sternal healing are common. The sternotomy wound may be complicated with partial or complete sternal dehiscence and sternal wound infection, osteomyelitis or even mediastinitis. Surgical site infection (SSI) involving the sternum is a distressing complication in cardiac surgery. The incidence of postoperative superficial and deep SSI in cardiac surgery varies from 1.3 to 12.8%.

Subsequent to median sternotomy, bone wax has been applied for decades as a mechanical barrier to maintain the haemostasis on the surface edges of the sternum. Bone wax is a nonabsorbable substance and it is believed that bone wax may cause inflammation as it is produced foreign body reaction and mechanically inhibit osteoblastic activity, which may eventually lead to increased risk of postoperative sternal dehiscence. Apparently, the use of bone wax has no clear recommendation in any guidelines and there are still controversies regarding the efficacy and safety of the application of bone wax.

To overcome the problem that may be related to the use of bone wax. Different innovative approaches are evaluated, including, a non-woven material to protect the sternum during operation. Sternum Guard™ is a single use, sterile surgical drape, for sternal protection,

with modified cellulose designed specifically to reduce the risk of surgical site infection. It is a sternal protection device that covers the sternum after median sternotomy and has specific mechanical protection that prevents lesions on the sternum. It is made from a non-woven material. Sternum Guard™ provides haemostatic effect through a natural reaction to compression and blood absorption. Moreover, it decreased the bacterial proliferation by decreasing the pH. The Sternum Guard™ covers the entire incision angle and subcutaneous tissue and it has very low particle release. It is easy to use and maintains a dry surgical site. 

However, there are still insufficient evidence to support the use of modified cellulose non-woven material in cardiac surgery. Thus, in this study we would like to compare the efficacy of Sternum Guard™ as opposed to Bone wax in post cardiac surgery patients.

## **1.2 Research Problem Formulation**

There is a deficient of evidence to verify the efficacy of Sternum Guard™ in reducing the rates of surgical site infection and sternal dehiscence in post cardiac surgery patients, specifically in Indonesian characteristic subjects. Thus, we would like to conduct this study to provide evidences regarding the use of Sternum Guard™.

## **1.3 Research Questions**

Is Sternum Guard™ more effective than Bone Wax application intraoperatively in reducing surgical site infection and sternal dehiscence for post cardiac surgery patients?

## **1.4 Hypothesis**

We hypothesize that Sternum Guard™ is more effective than Bone Wax in reducing surgical site infection and sternal dehiscence for post cardiac surgery patients.

## **1.5 Objectives**

### **Overall Objective:**

The aim of the research is to compare the efficacy of Sternum Guard™ as opposed to bone wax in post cardiac surgery patient.

**Specific Objectives:**

1. To compare the surgical site infection and sternal dehiscence rates at the end of hospital stay, day 14 post operation, and day 30 post operation in post cardiac surgery patient with the application of Sternum Guard™ as opposed to bone wax intraoperatively.
2. To compare the haemostasis effect of Sternum Guard™ as opposed to bone wax intraoperatively in cardiac surgery.
3. To compare the satisfaction rate (includes global satisfaction rate, haemostasis and dryness of surgical site, and mechanical protection) of the surgeons who are using the Sternum Guard™ as opposed to bone wax intraoperatively in cardiac surgery.

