### **3.6 Data extraction**

Every participant included in this study will be scheduled for any cardiac surgery electively. Every participant will undergo the surgery with cardiopulmonary bypass. All of the surgery will be conducted in a similar manner, however, if there is any complication intraoperatively, every action will be taken according to the situation and will be recorded. Before incision the Sternum Guard™ and sterile drapes for the bone wax group will be weighed. After median sternotomy, the surgeons will be given Bone Wax or Sternum Guard™ to be applied to the sternum. The decisions will be made based on the block randomisation technique and will be informed beforehand to the nurse scrub and the surgeon. In the Bone Wax group, cauterization will be used according to the sternum's condition and surgeon's decision before applying the sterile draping and after removing it if needed. In the Sternum Guard™ group, cauterization will also be applied before inserting it to the sternum and after removing the Sternum Guard™ if needed.

Subsequent to median sternotomy, sternal bleeding will be assessed. In the Sternum Guard™ group, immediately before cauterization and in Bone Wax group right before applying the bone wax.

Once the surgery is done, the Sternum Guard™ and the sterile drapes will be weighed again. Sternal trauma will be evaluated at the end of surgery (visible trauma or no visible trauma). In the Sternum Guard™ group, within 5 minutes of Sternum Guard and sternal retractors removal and on the Bone Wax group within 5 minutes of removal of the sterile drapes and sternal retractors. Another sternal bleeding assessment will be done on both groups. In the Sternum Guard™ group it will be assessed immediately after removing the Sternum Guard, before the cauterization, while on the Bone Wax group, before applying any bone wax and cauterization. The sternotomy wound will be evaluated and documented at Day 0, at the end of hospital stay, Day 14 post - operative, and Day 30 post-operative. After the surgery, the surgeons will be given questionnaire regarding the use of Sternum Guard™ as opposed to Bone Wax.

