### **3.8 Variable identification**

Independent variable in this study included the patient that are eligible for cardiac surgery. Dependent variable in this study are the assessment of surgical site infection and sternal dehiscence, haemostasis effect in Sternum Guard™ and Bone Wax group, and satisfaction rates of the surgeons.

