### **3.10 Clinical outcome indicators and assessments**

1. Surgical site infection: assessment of the surgical site infection includes the types of infection (deep and superficial), sternal dehiscence, and percentage of the surgical site infection and sternal dehiscence. The participants will be assessed at day 0, at the end of the hospital stay, day 14 post - operative, and day 30 – post operative. All of the sternotomy wound will be documented digitally at day 0, at the end of the hospital stay, day 14 post – operative, and day 30 post-operative.

2. Haemostasis effect: It will assess the quantity of blood lost from the sternal edges in Sternum Guard™ and Bone Wax group. The Sternum Guard™ and sterile drapes will be weighed before and after surgery to estimate the blood lost.
  
3. Satisfaction Rate: The satisfaction rate will be evaluated using a questionnaire distributed to the surgeons. The questionnaire will contain overall satisfaction, ease of placement, maintenance of a dry field throughout the surgery, ease of removal; each of this question will have four different response which are satisfied, fairly satisfied, fairly dissatisfied, dissatisfied. Additionally, the surgeons will be asked about the experience in using Sternum Guard™ as compared to Bone Wax and it will contain 3 different response: worse, similar, better.

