#### B. Treatment Group with Sternum Guard™:

Group of patients who undergo cardiac surgery with the use of cardiopulmonary bypass and use Sternum Guard™ to protect the sternum after median sternotomy.

Table 1 - Table of Operational Definition

	Variable	Definition	Type of Data	Code
1	Age	The age of participant when undergo the cardiac surgery, it defines with calculated birth year taken from the medical record	Numerik	
2	Gender	Gender which is included in this study are based one the	Categorical	1 = Male 2 = Female

		data recorded in the medical record.		
3	Comorbid	Data extracted from anamnesis and the medical record, with blood pressure $\geq 140/90$ mmHg and diabetes mellitus (Fasting Blood Glucose $>126$ mg/dL or 2 hr post prandial blood glucose or one time blood glucose $>200$ mg/dL)	Categorical	1 = Yes 2 = No
6	Cardiac Surgery	Any cardiac surgery that are conducted in adult cardiac surgery division which are using cardiopulmonary bypass	Categorical	1 = CABG 2 = Valve 3 = CABG + Valve 4 = Vascular
7	Surgical Site Infection	Surgical site infection is divided by 2 categories (Superficial: infection occurs just in the area where the incision is made; Deep: occurs beneath the incision area in muscle and the tissues surrounding the muscle). It is evaluated at day 0, at the end of hospital stay, day 14 post – operative and day 30 post-operative	Categorical	1 = Deep 2 = Superficial
8	Sternal Dehiscence	Occurs when there is an evidence of sternum separation. Often	Categorical	1 = Yes 2 = No

[figure not shown]
		accompanies with mediastinitis.		
9	Haemostasis Effect	The data obtained by quantity of blood lost from the sternal edges in Sternum Guard TM and Bone Wax group. The Sternum Guard TM and sterile drapes will be weighed digitally before and after surgery to estimate the blood lost.	Numeric	
10	Satisfaction Rate	The result obtained by the questionnaire in both groups.  Overall satisfaction rate  Maintenance of a dry surgical field during intervention (both groups)  Haemostatic effect  Ease of insertion (Sternum Guard TM group)  Ease of removal (Sternum Guard TM group)	Categorical	1 = Satisfied 2 = fairly satisfied 3 = fairly dissatisfied 4 = dissatisfied
12	Experience satisfaction rate	The result obtained by the questionnaire for the Sternum Guard TM group.	Categorical	1 = worse 2 = similar 3 = better

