**Questionnaire for the Surgeons**  
**Efficacy of Sternum Guard™ in comparison of Bone Wax in Post Cardiac Surgery**  
**Patient: A Single Blind, Single Centre, Randomized Control Trial**  
 Research Principles: dr. [name], B.MedSc. ; Dr. dr. [name], Sp. BTKV (K) MARS.

Please tick (√) the box accordingly; Please leave your comment(s)

Section 1 (Sternum Guard)	Surgeon's Satisfaction with Sternum Guard				
	Satisfied	Fairly Satisfied	Fairly Dissatisfied	Dissatisfied	Comments
Overall Satisfaction					
Ease of placement					
Maintenance of a dry field throughout the surgery					
Haemostasis effect					
Ease of removal					
Section 2	Surgeon's Experience in using Sternum Guard as opposed to Bone Wax				
	Worse	Similar	Better		Comments
Experience of the surgeon in using Sternum Guard as compared to Bone Wax					

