## Questionnaire for the Surgeons

**Efficacy of Sternum Guard™ in comparison of Bone Wax in Post Cardiac Surgery**

**Patient: A Single Blind, Single Centre, Randomized Control Trial**

Research Principles: dr. [name], B.MedSc. ; Dr. dr. [name], Sp. BTKV (K) MARS.

Section 1 (Bone Wax)	Surgeon's Satisfaction with Bone Wax				Comments
	Satisfied	Fairly Satisfied	Fairly Dissatisfied	Dissatisfied	
Overall Satisfaction					
Ease of placement					
Maintenance of a dry field throughout the surgery					
Haemostasis effect					
Ease of removal (if any)					

Comment (s):

1.

Time and Date:  
Investigator:

Group:  
Patient's initial:

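### Objective 3 includes surgeon satisfaction with mechanical protection, but neither questionnaire asks about it; separately, visible sternal trauma is recorded in both arms without being named as an outcome.

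*Combined protocol and SAP*

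**What the plan says.** **Objective.** Specific Objective 3 in section 1.5 sets out to compare the satisfaction of surgeons using the two products. Besides the global rating it names "haemostasis and dryness of surgical site, and mechanical protection".

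**Instruments.** Section 3.10 describes the form: "The questionnaire will contain overall satisfaction, ease of placement, maintenance of a dry field throughout the surgery, ease of removal". The two forms in the appendix add a haemostasis item, which makes five rated items each. The dry-field row, "Maintenance of a dry field throughout the surgery", is identical on both. The bone wax form has been adapted to its product, with a row reading "Ease of removal (if any"). The Sternum Guard form alone has a second section with a single worse/similar/better question: "Experience of the surgeon in using Sternum Guard as compared to Bone Wax". In section 3.11, row 10 of Table 1 defines the satisfaction rate by an overall rating, "Maintenance of a dry surgical field during intervention (both groups"), haemostatic effect, insertion and removal.

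**Sternal trauma.** Section 3.6 states: "Sternal trauma will be evaluated at the end of surgery (visible trauma or no visible trauma"). The assessment is made in both arms within five minutes of taking out the retractors and the device or drapes. The outcome list in section 3.8 reads "Dependent variable in this study are the assessment of surgical site infection and sternal dehiscence, haemostasis effect in Sternum Guard™ and Bone Wax group", followed by surgeon satisfaction.

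**The concern.** An objective can be answered only if some instrument collects the data for it. Here the objective commits the trial to a between-arm comparison of four things, and the forms supply three. Surgeons rate each case after the operation, so a rating that was not on the form cannot be reliably reconstructed later.

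The trauma record raises a related but different issue. The Abstract and section 1.1 say that the device protects the bone mechanically and prevents sternal lesions. The trial records a binary finding that bears directly on that claim, in both arms, but does not say that it is an outcome or how it will be reported. A comparison made later would be post hoc, and a reader could not tell whether it was reported because of how it turned out.

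**Working it through.** No design figure depends on this point, so the main check sets the objective beside each place where data are defined or collected.

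**Step 1: satisfaction components.**

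| Component in Objective 3 | 3.10 description | Table 1, row 10 as shown | Sternum Guard form | Bone Wax form |
|---|---|---|---|---|
| Global satisfaction | yes | yes | yes | yes |
| Haemostasis | no | yes | yes | yes |
| Dryness | yes | yes | yes | yes |
| Mechanical protection | no | no | no | no |

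Haemostasis is missing from the 3.10 description, but no data are lost because both forms ask about it. Mechanical protection is missing from all four places: 0 of 5 rated items on each form.

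**Step 2: could something else on the forms stand in?** The free-text comments are not a structured rating. The second section of the Sternum Guard form is one global question and has no counterpart on the bone wax form. Neither gives a rating of mechanical protection in both arms.

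**Step 3: where trauma is named as an outcome.** Section 3.8: no. Section 3.10: no. Table 1 as shown: no. Table 3 (outcome dummy table): no. That is 0 of 4.

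**Step 4: how many patients are involved (context only).** Section 3.7 uses P1 = 0.15, P2 = 0.05, two-sided α = 5% and power 90%, so the mean proportion is 0.10.

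- First term: 1.960 × √(2 × 0.10 × 0.90) = 1.960 × 0.4243 = 0.8315
- Second term: 1.2816 × √(0.15 × 0.85 + 0.05 × 0.95) = 1.2816 × 0.4183 = 0.5361
- n per arm = (0.8315 + 0.5361)² / 0.10² = 1.870 / 0.01 ≈ 187.05, rounded up to 188
- Total = 2 × 188 = 376, which agrees with the plan
- With the plan's dropout allowance: 376 × 1.10 = 413.6, rounded up to 414, which also agrees

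Trauma is assessed in theatre, before losses to day-30 follow-up. It could therefore be available for up to the 414 planned patients, not only 376.

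**The case against.** The strongest reply is that little is lost. The research question and hypothesis (1.3 and 1.4) concern infection and dehiscence only, and the sample size does not rest on satisfaction. Three of the four components are on both forms. Since 3.10, Table 1 as shown and the forms all omit mechanical protection, the phrase in Objective 3 is the outlier and could simply be deleted. This stands as an argument about weight and as an alternative repair. It does not remove the mismatch.

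Several stronger readings are tempting, and the documents do not support them:

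- **The trauma data will be discarded or left unanalysed.** Section 3.9 says that all collected data will be analysed, and it provides chi-square or Fisher's exact tests for categorical comparisons between the arms. What is missing is a named, pre-specified outcome.
- **The trauma gap is why Objective 3 fails.** Trauma is a physical finding, while Objective 3 concerns satisfaction. Listing trauma would not supply the missing rating, and its absence is not what leaves that component unanswerable.
- **Mechanical protection is the device's main claimed mechanism.** Section 1.1 also claims haemostasis, lower pH with less bacterial growth, coverage of the incision and a dry site, and does not rank them.
- **Trauma is the more objective measure.** Section 3.6 names no assessor and no criterion for visible trauma, and section 3.5 states that surgeons are unblinded.
- **Table 1 certainly has no trauma row.** The available text of Table 1 skips rows 4, 5 and 11 and contains a figure that is not shown. This may be misnumbering or lost text. The conceptual framework and research flow diagrams are also not visible.

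**Conclusion.** The point holds in two separate parts. First, surgeon satisfaction with mechanical protection, one of the four components of Objective 3 (one of three if haemostasis and dryness are taken together, as the objective groups them), has no item on either form and cannot be compared between arms. Second, visible sternal trauma is recorded in both arms and bears on a stated claim for the device, but is not named as an outcome in 3.8, 3.10, Table 1 as shown or Table 3, so its comparison is possible but not pre-specified.

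The first part rests on the two forms, which are legible item by item. The second is subject to the possible gaps in Table 1, although 3.8, 3.10 and Table 3 do not share that doubt. Global satisfaction, haemostasis and dryness remain answerable, and the primary infection and dehiscence comparison is untouched. The change is worth making because it is nearly free and the missing rating cannot be recovered after surgery; it does not threaten the trial's main conclusion.

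**What to change.** Before enrolment:

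1. Add a mechanical-protection row, on the existing four-level scale, to both questionnaires, and add the same item to the satisfaction content in 3.10 and to row 10 of Table 1.
2. Name visible sternal trauma (yes/no) in 3.8, 3.10, Table 1 and Table 3, compared between arms by chi-square or Fisher's exact test as 3.9 already allows. In Table 3 put it under a new secondary-outcomes heading, because the only heading there now is for primary outcomes.
3. Describe trauma as a direct measure of protection and not of satisfaction, say who rates it, and note that the surgeons are unblinded.

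The cost is one row on each form, a row or line in each table and section named, and one more secondary comparison. No new procedure is needed, since trauma is already assessed.

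If the sponsor does not want the satisfaction item, deleting mechanical protection from Objective 3 would restore consistency, at the price of giving up that component. Naming trauma as a secondary outcome would still be worthwhile.

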**1.6 Benefit of the Study****1.6.1 Academic Aspect**

This study is expected to benefit academically by providing an answer as well as justification on the efficacy of Sternum Guard™ in post cardiac surgery patient in comparison with bone wax intraoperatively.

**1.6.2 Clinical Aspect**

This study is believed to have impact clinically in reducing surgical site infection and sternal dehiscence in post cardiac surgery patients. By reducing the surgical infection and sternal dehiscence rates it would reduce the morbidities and mortalities rates as well.

**1.6.3 Research Aspect**

This study could be the foundation of another study in evaluating which aspects that could lead to surgical site infection and sternal dehiscence post cardiac surgery. Additionally, it could identify another effective method to reduce the percentages of surgical site infection and sternal dehiscence in post cardiac surgery patients.

## **Chapter 2**

### **Literature Review**

#### **2.1 Sternum anatomy**

Interestingly, the anatomy and physiology of the chest wall and sternum are completely entangled. The musculoskeletal structure of the chest wall and sternum are served to give protection to the lungs and thoracic viscera. The structure of the skeletal of the thorax consists of 12 pairs of ribs and their cartilages, 12 thoracic vertebrae, the intervertebral discs, and the sternum.

The sternum lies in the anterior midline. It is an elongated and flat bone and has approximately 15 to 20 cm long. It is structured from the cartilaginous precursors that ossify separately to form the components in which divided by three parts: the manubrium, the body, and the xyphoid process.

The first part is the manubrium, it is about 5 cm wide in its upper half and around 2.5 to 3 cm wide in its lower half. The upper border of the manubrium is solidified and marked on either side by a notch for articulation with the clavicle. Ventrally, an indentation is present together with the sternal ends of each of the clavicle, it forms the jugular or the suprasternal notch. The widest part is distinct by the bilateral indentations, the costal incisura, in which to accommodate articulation of the first costal cartilage.

The second part is the body of the sternum. It is the longest part and slightly more than twice the length of the manubrium. It is skewed at a steeper angle than the manubrium and its articulation with that bone forms the angle that is called the sternal angle. The lateral side of the body expose segmental incisura for articulation of coastal cartilage 2 to 7. This part ends a about the level of the 10th or 11th of thoracic vertebrae, where it forms a cartilaginous joint with the xyphoid process.

The last part of the sternum called the xyphoid process. It is the shortest and thinnest part of the sternum. Occasionally, this part is bifid or perforated.

The blood supply to the sternum has been studied repeatedly over the past decades especially its association with the notorious complication in sternotomy wound healing. The major source of arterial branches to the sternum is the internal thoracic or mammary artery (ITA or IMA). It originates from the subclavian artery directly or sometimes from a common trunk with another artery of the thyrocervical trunk. Before entering the mediastinum, it crosses the phrenic nerve either dorsally or ventrally. It descends 1–2 cm from the lateral margin of the sternum adjacent to the posterior aspect of the chest wall, partly covered by the transversus thoracic muscle from the third to the sixth costal cartilage.

Blood supply to the sternum originate either directly from the medial aspect of the ITA (non-collateral branches) or from short trunks that also give rise to perforating branches to the intercostal and pectoral muscles and overlying skin or to anterior intercostal rami. Sternal blood supply branches are intersegmental, means that it is located in the intercostal spaces and form arcades at the lateral edge of the sternum. It is also more frequent in cranial than in caudal segments, particularly in the second and third intercostal space.

Based on the blood supply anatomy it is evident that harvesting of the ITA or IMA for coronary bypass surgery will interrupt the sternal circulation to some extent. Therefore, when the ITA or IMA is dissected, any branches should be ligated as close as possible to the main vessel in order to preserve the collateral branches.

